6.2 DETAILS OF TRIAL PROCEDURES AT SELECTED VISITS

6.2.1 Screening and run-in period

Trial procedures to be performed during the screening period can be found in the [Flow Chart A](#). Screening period is defined as the time between the date of informed consent (or the screening consent) to the date of first dose (visit 2). No trial procedures should be performed until the patient has consented to take part in the trial. The separate screening consent is to allow collection of the first morning void urine sample to obtain the UPCR needed to check eligibility criteria (section [3.3.2](#) and [8.1](#)). Each patient will be assigned a unique patient number and enrollment will be recorded in eCRF.

For patients participating in the trial via the DCT model, the consenting process may be completed electronically (via eConsent) within the DCT Platform. Screening consent when applicable will be administered outside the DCT Platform. Prior to initiating the eConsent process, eligibility of potential patients will be assessed after review of medical records by the investigator or site staff. Once this preliminary eligibility is confirmed, a study informed consent discussion will be scheduled. The informed consent materials will be presented in the DCT Platform. The patient will review the documents and during this telephone call with the investigator or designee will have the opportunity to discuss the study, and have their questions answered. If patient agrees to participate in the trial, an electronic signature will be obtained.

Once the patient has consented to collect the first morning void urine sample for screening purposes, the patient is considered to be enrolled in the trial. The patient should be recorded on the enrollment log and be registered in the IRT.

Baseline conditions, medical history, and eligibility criteria will be assessed at visit 1. Concomitant therapy and AE (if any) will be recorded. At the conclusion of visit 1, patients should receive instructions on procedures to be followed during the screening period.

If all the eligibility criteria are met, randomization will be completed by calling the IRT. Randomization will initiate trial medication shipment to the patient and visit 2 will be scheduled. For more information on medication administration, see section [4.1.4](#).

Screening period may be extended for administrative reasons with approval from the CT Manager.

If screening period exceeds 30 days, the investigator should review the laboratory reports from the screening visit (visit 1) and make a determination if any labs specified in the protocol must be repeated before the first dosing visit. If deemed necessary, test samples should be drawn and sent to the central laboratory.

Clinical Trial Protocol

Proprietary confidential information © 2025 Boehringer Ingelheim International GmbH or one or more of its affiliated companies

Discontinuation during the screening period

If patients discontinue from the trial during the screening period, no additional study visits are required, and they will be marked as screen failures. Patient will be registered as a screen failure in IRT.

Rescreening and retesting

Patients who screen failed due to a reason that was reversible and has since been resolved or those who were screen failed for administrative reasons (e.g., extended travel, life events) may be rescreened once with approval from the CT Manager or designee.

If the investigator believes that a lab test result is due to an error or other extenuating circumstances, the lab test can be repeated once without the patient having to be rescreened.

6.2.2 Treatment period.

Treatment period will begin at visit 2 and will continue for 12 weeks. Procedures to be completed at each study visit can be found in the [Flow Charts A](#) and [B](#). There will be three phone call visits during the treatment period: visits 3A, 4A, and 5A. Please refer to Flow Chart B for details on the phone call visits.

Unscheduled visits may be arranged if necessary. Procedures completed during an unscheduled visit will depend on the circumstances under which the visit was scheduled, and at the discretion of the investigator.

EoT must be rescheduled if the 24-hour urine sample is not collected for UPCR measurements. After completion of the treatment period, the patient will enter the 30-day follow-up period.

Discontinuation during the treatment period

For discontinued patients, EoT visit must be scheduled as soon as possible. After completion of the EoT visit, patient will complete both follow-up visits (FUP1 and EoS).

6.2.3 Follow-up period and trial completion

The 30-day follow-up period extends from the EoT visit until the EoS phone call visit. The FUP1 visit should be scheduled 7 days after the EoT visit, and EoS phone call visit should be scheduled 30 days after the EoT visit. The EoS visit will be a telephone visit for all patients. For patients participating in the trial remotely, the study site staff will complete EoS visit by telephone. Procedures to be completed at the follow-up visits can be found in the [Flow Chart A](#). Investigator should ensure that eye exams (if applicable) are completed as part of the EoS visit and the results are reviewed.

Clinical Trial Protocol

Proprietary confidential information © 2025 Boehringer Ingelheim International GmbH or one or more of its affiliated companies

The last study visit will be the EoS visit and this will mark the end of observation period, and the patient has completed the trial.

Clinical Trial Protocol

Proprietary confidential information © 2025 Boehringer Ingelheim International GmbH or one or more of its affiliated companies

7. STATISTICAL METHODS AND DETERMINATION OF SAMPLE SIZE

7.1 NULL AND ALTERNATIVE HYPOTHESES

No confirmatory testing will be performed and hence no null and alternative hypotheses are defined since this is a non-confirmatory study.

7.2 PLANNED ANALYSES

7.2.1 General considerations

The following analysis sets will be defined for statistical analyses:

- Entered Set (ES): This patient set includes all patients who signed informed consent. The ES will be used for the analysis of patient disposition.
- Randomized Set (RS): This patient set includes all patients who signed the informed consent form and were also randomized, regardless whether the patient was treated with trial medication or not.
- Treated Set (TS): This patient set includes all patients who received at least one dose of trial medication. The TS is used for safety analyses as well as demographics and baseline characteristics.
- Full Analysis Set (FAS): This patient set includes all patients who were randomized and treated with evaluable measurements UPCR at baseline and at least one UPCR measurement after first dose. The FAS is the main analysis set for the analysis of efficacy.
- Pharmacokinetic Analysis Set (PKS): This patient set includes all patients in the TS who provide at least one PK endpoint that was not excluded due to protocol violation relevant to the evaluation of PK or due to PK non-evaluability.

For the analysis of efficacy, patients will be analyzed as randomized, without regard to any treatment changes.

7.2.2 Handling of Intercurrent Events

An intercurrent event (ICE) is defined as an event of,

- early discontinuation,
- lost to follow-up, or
- death.

The strategies for handling intercurrent events in this trial are as follows:

Clinical Trial Protocol

Proprietary confidential information © 2025 Boehringer Ingelheim International GmbH or one or more of its affiliated companies

- Hypothetical estimand: assuming all subjects remained adherent to the assigned trial medication and the study protocol. This strategy will include all data collected until time of an ICE.
- Treatment policy estimand: using all available data including data collected after an ICE.

7.2.3 Primary endpoint analyses

An exploratory inferential analysis for the primary endpoint, in terms of proportion of patients achieving at least 25% UPCR reduction relative to baseline at 12 weeks, will be conducted by providing 95% confidence intervals from each treatment group. The primary estimand of interest is the treatment effect assuming all subjects remained adherent to the assigned trial medication and the study protocol using a hypothetical approach, i.e., study drug is taken as directed. This analysis will include all data collected until time of an ICE.

In addition, an analysis of variance (ANOVA) model (for the UPCR change from baseline at week 12) will be used to see difference across arms. Dose-response relationship based on reduction in log of UPCR may be explored using graphical approach.

7.2.3.1 Sensitivity analyses

Sensitivity analyses to be conducted to assess the robustness of the primary analysis outcome will be described in the trial statistical analysis plan (TSAP).

7.2.3.2 Supplemental analysis of primary endpoint

An additional assessment of the primary endpoint will be conducted using the treatment policy estimand, i.e., effectiveness/intention to treat. The treatment policy estimand will use all available data including data collected after an ICE. All attempts will be made to collect all data per protocol.

[figure not shown]
7.2.3.3 Subgroup analyses

No subgroup analysis planned.

7.2.4 Secondary endpoint analyses

[figure not shown]
All secondary endpoints in Section [2.1.3](#) except pharmacokinetic parameters of BI 764198 will be analysed by using descriptive statistics and figures.

Further details will be given in the TSAP.

Clinical Trial Protocol

Proprietary confidential information © 2025 Boehringer Ingelheim International GmbH or one or more of its affiliated companies

7.2.6 Safety analyses

Adverse events will be coded using the Medical Dictionary for Drug Regulatory Activities (MedDRA). Standard BI summary tables and listings will be produced. All adverse events with an onset between start of treatment and end of study, which include a 5-day period after last dose of trial medication, will be assigned to the on-treatment period for evaluation.

[figure not shown]
All treated patients (i.e., all patients who received at least one dose of trial medication) will be included in the safety analysis. In general, safety analyses will be descriptive in nature and will be based on BI standards. No hypothesis testing is planned.

Statistical analysis and reporting of adverse events will concentrate on treatment-emergent adverse events, i.e. all adverse events occurring between start of treatment and end of the study. Adverse events that start before first intake of trial medication and deteriorate under treatment will also be considered as 'treatment-emergent'.

Frequency, severity, and causal relationship of adverse events will be tabulated by system organ class and preferred term after coding according to the current version of the MedDRA at the database lock.

Laboratory data will be analyzed both quantitatively as well as qualitatively. The latter will be done via comparison of laboratory data to their reference ranges. Values outside the reference range as well as values defined as clinically relevant will be summarized. Treatment groups will be compared descriptively with regard to distribution parameters as well as with regard to frequency and percentage of patients with abnormal values or clinically relevant abnormal values.

Vital signs, physical examinations, or other safety-relevant data observed at screening, baseline, during the course of the study and at the end-of-study evaluation will be assessed with regards to possible changes compared to findings before start of treatment.

Clinical Trial Protocol

Proprietary confidential information © 2025 Boehringer Ingelheim International GmbH or one or more of its affiliated companies

7.3 HANDLING OF MISSING DATA

No missing data will be imputed in the UPCR, [REDACTED], and urinary protein excretion, analyses. Handling of missing PK data will be performed according to the relevant Corporate Procedure. PK parameters that cannot be reasonably calculated based on the available drug concentration-time data will not be imputed. Further details will be specified in the TSAP.

7.4 RANDOMIZATION

The study will be performed as a double-blind design with respect to the 3 different doses of BI 764198 and placebo in a 1:1:1:1 ratio stratified by use of corticosteroids. Patients will be randomized in blocks to double-blind treatment via the IRT system.

Clinical Trial Protocol

Proprietary confidential information © 2025 Boehringer Ingelheim International GmbH or one or more of its affiliated companies

The sponsor will arrange for the randomization as well as packaging and labelling of trial medication. The randomization list will be generated using a validated system that uses a pseudo-random number generator and a supplied seed number so that the resulting allocation is both reproducible and non-predictable.

7.5 DETERMINATION OF SAMPLE SIZE

To explore the clinical principle of BI 764198 it is planned to include a total of 60 patients with FSGS. The planned sample size is not based on a power calculation. The size of 15 patients per treatment arm is considered to be sufficient to detect differences between the different treatment groups and placebo in terms of the primary endpoint.

The goal of the trial is to determine if the difference in UPCR response between at least one dose after baseline and placebo is greater than 25%. Assuming that approximately 40%, 30%, 20% of patients in 80mg, 40mg, 20mg treatment groups, respectively, achieve at least 25% UPCR reduction at 12 weeks while 9 % of patients in placebo group achieve 25% UPCR reduction, the proposed sample size provides 73.4% probability for the difference in responder rates between at least one treatment arm and placebo to be greater than 25%.

Calculations were performed using R3.6.1.

Clinical Trial Protocol

Proprietary confidential information © 2025 Boehringer Ingelheim International GmbH or one or more of its affiliated companies

8. INFORMED CONSENT, TRIAL RECORDS, DATA PROTECTION, PUBLICATION POLICY, AND ADMINISTRATIVE STRUCTURE

The trial will be carried out in compliance with the protocol, the ethical principles laid down in the Declaration of Helsinki, in accordance with the ICH Harmonized Guideline for GCP, relevant BI SOPs, the EU directive 2001/20/EC /EU regulation 536/2014, and other relevant regulations. Investigators and site staff must adhere to these principles. Deviation from the protocol, the principles of ICH GCP or applicable regulations as will be treated as “protocol deviation”.

Standard medical care (prophylactic, diagnostic and therapeutic procedures) remains the responsibility of the treating physician of the patient.

The investigator will inform the sponsor immediately of any urgent safety measures taken to protect the trial patients against any immediate hazard, as well as of any serious breaches of the protocol or of ICH GCP.

The BI transparency and publication policy can be found on the following web page: trials.boehringer-ingelheim.com. The rights of the investigator and of the sponsor with regard to publication of the results of this trial are described in the investigator contract. As a rule, no trial results should be published prior to finalisation of the Clinical Trial Report.

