7.4 PRIMARY OBJECTIVE ANALYSIS

7.4.1 Primary analysis of the primary endpoint(s)

This is an exploratory trial. No confirmatory testing is performed and hence neither null nor alternative hypotheses are defined. Nominal p-values may be presented. The FAS will be used for the analysis of the primary endpoint.

An exploratory analysis for the primary endpoint, in terms of proportion of patients achieving at least 25% UPCR reduction relative to baseline at week 12 (patients missing the week 12, 24-hr UPCR will be counted as non-responders) will be conducted by providing 95% confidence intervals from each treatment group, via logistic regression utilizing corticosteroid use at randomization (variable CORTIC) and baseline 24-hr UPCR, as covariates. The baseline UPCR will be from the average of two 24-hour urine samples collected before visit 2 (before the first dose). Graphical representations of change in 24-hour UPCR from baseline will also be presented.

The primary estimand of interest is the treatment effect, assuming all subjects remained adherent to the assigned trial medication, and the study protocol using a hypothetical approach, i.e., study drug is taken as directed. This analysis will include all data collected until time of an ICE. For primary analysis, UPCR measurements after ICE will not be included. ICE and the strategies for handling intercurrent events are defined in the CTP section 7.2.2 and [section 6.3](#), above, as follows:

An intercurrent event (ICE) is defined as an event of,

[figure not shown]
- Early discontinuation,
- Lost to follow-up, or
- Death.

The strategies for handling intercurrent events in this trial are as follows:

- (1) Hypothetical estimand: assuming all subjects remained adherent to the assigned trial medication and the study protocol. This strategy will include all data collected until time of an ICE.
- (2) Treatment policy estimand: using all available data including data collected after an ICE.

For this analysis only the Hypothetical estimand will be considered.

In addition, an analysis of covariance (ANCOVA) model (for the UPCR change from baseline at week 12) will be used to see differences across arms, with corticosteroid use at randomization and baseline 24-hr UPCR, as covariates. Dose-response relationship based on reduction in log of UPCR may be explored using a graphical approach.

[figure not shown]

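### The goal of determining a difference above 25 points rests on the largest of three observed differences against one 15-patient placebo arm, and the visible analysis plans no interval for that difference

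*Protocol*

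**What the plan says.** Protocol 7.5 states the goal as "to determine if the difference in UPCR response between at least one dose after baseline and placebo is greater than 25" per cent. The rates are set out as follows: "Assuming that approximately 40%, 30%, 20% of patients in 80mg, 40mg, 20mg treatment groups" respectively reach the 25% UPCR reduction, "while 9 % of patients in placebo group achieve 25% UPCR reduction". On these inputs "the proposed sample size provides 73.4% probability", which the protocol defines as the "probability for the difference in responder rates between at least one treatment arm and placebo to be greater than 25" per cent. The same section says that the size is not based on a power calculation, yet also: "The size of 15 patients per treatment arm is considered to be sufficient to detect differences".

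Protocol 7.4 randomises "in a 1:1:1:1 ratio stratified by use of corticosteroids", so one placebo arm of about 15 serves all three comparisons.

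For the responder endpoint, Protocol 7.2.3 plans a 95% confidence interval for each treatment group. SAP 7.4.1 obtains it by logistic regression with corticosteroid use and baseline UPCR as covariates. The ANOVA (ANCOVA in the SAP) compares arms on change in UPCR, not on responder rate. SAP 7.4.1 adds: "No confirmatory testing is performed and hence neither null nor alternative hypotheses are defined. Nominal p-values may be presented".

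**The concern.** The goal is worded as a finding about a difference larger than 25 points. The supporting probability concerns something weaker, namely that the largest of three noisy observed differences exceeds 25 points. With 15 per arm these can diverge widely. The largest of three tends to overstate the true effect, and all three share the same placebo sampling error.

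Section 7.5 shows only how often the criterion is met when the drug works as hoped. It gives no figure for a smaller effect or for none. The visible primary analysis does not fill the gap, because it plans no interval for the quantity that the goal names. At stake is the reading of a proof-of-principle result: an observed best difference just above 25 points could be reported as having met the goal when the data are also compatible with little or no effect.

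**Working it through.** **Inputs.** 15 per arm; placebo responder rate 9%; active rates 40/30/20%; threshold 25 percentage points (all Protocol 7.5); one placebo arm (Protocol 7.4). Assumed, not in the documents: a true gain of 10 points on every dose, a graded response of 12/16/19%, placebo rates of 20% and 30%, and dropout rates.

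**What the criterion means.** 3/15 = 20.0 points and 4/15 = 26.7 points, so exceeding 25 points requires at least 4 more responders than placebo.

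**Formula.** With K placebo responders and X_d responders on dose d:

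P(met) = Σ_k P(K = k; 15, p0) × [1 − Π_d P(X_d ≤ k + 3; 15, p_d)]

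**The plan's own figure.** With 40/30/20% against 9% this gives 80.7%, not 73.4%. A normal approximation gives 76.7%. Values near 73.4% need assumptions that 7.5 does not state: placebo fixed at 9% without sampling error (72.7%), 10% dropout counted as non-response (74.5%), or 13 evaluable per arm (72.2%). The method behind 73.4% should therefore be stated. The point here does not depend on which figure is right.

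**Every dose truly adds 10 points (19% against 9%).**

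| k | P(K = k) | P(X ≤ k + 3) | 1 − cube | product |
|---|---|---|---|---|
| 0 | 0.2430 | 0.6854 | 0.6780 | 0.1648 |
| 1 | 0.3605 | 0.8606 | 0.3627 | 0.1307 |
| 2 | 0.2496 | 0.9510 | 0.1400 | 0.0349 |
| 3 | 0.1070 | 0.9863 | 0.0405 | 0.0043 |
| 4 or more | | | | 0.0003 |

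The sum is 0.335. About half comes from trials with no placebo responder. Replacing the cube by a single dose gives 0.141, so taking the best of three multiplies the rate by 33.5/14.1 = 2.4.

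**Other scenarios, same formula.**

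| Placebo rate | No effect, best of 3 | No effect, one dose | +10 on all, best of 3 | +10, one dose |
|---|---|---|---|---|
| 9% (protocol) | 3.8% | 1.3% | 33.5% | 14.1% |
| 20% (assumed) | 13.6% | 5.4% | 41.0% | 19.7% |
| 30% (assumed) | 18.9% | 8.1% | 43.4% | 22.1% |

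At 9% placebo:
- graded response 12/16/19%: 22.7%;
- one dose adds 10 points and the others nothing: 15.9%;
- +10 on all doses with 10% or 20% dropout counted as non-response, as SAP 7.4.1 specifies: 28.3% or 22.9%.

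**Size of the overstatement.** By simulation, with +10 on all doses and 9% placebo, the mean observed best difference is 18.6 points over all trials and 31 points in trials that meet the criterion.

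**What an interval would show.** Take a result that just meets the criterion, 5/15 against 1/15. The 95% Wilson limits are 0.152 to 0.583 and 0.012 to 0.298. Newcombe's interval for the difference of 0.267 is:
- lower: 0.267 − √[(0.333 − 0.152)² + (0.298 − 0.067)²] = −0.03;
- upper: 0.267 + √[(0.583 − 0.333)² + (0.067 − 0.012)²] = 0.52.

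The result is compatible with anything from no benefit to about 50 points, before any allowance for selection.

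**The case against.** The strongest reply is that no pass rule exists. Section 7.5 gives a goal and a probability in a sample-size rationale. Nothing says that the trial succeeds or that a dose advances if the observed best difference exceeds 25 points. The trial is declared non-confirmatory in Protocol 7.1 and SAP 7.4.1, and Protocol 4.1.2 leaves dose finding to a dedicated later trial. This stands. A reader might infer a formal decision rule with an uncontrolled type I error, and hence a need for multiplicity control. The documents do not support that.

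Second, the one-third figure needs all three doses, over a fourfold range, to add the same 10 points, whereas the protocol assumes a graded response. This also stands: a graded alternative gives 22.7%, and no effect at the protocol's placebo rate gives only 3.8%. A true 10-point gain is moreover not an inactive drug.

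Third, selection is not the whole cause. One pre-named dose would still meet the criterion in 14.1% of trials, because the arms are small.

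Fourth, the SAP names MCP-Mod in its software paragraph and parts of it are redacted. A statement that no allowance is made for selection can cover only Protocol 7.5 and the visible SAP text, where nothing links MCP-Mod to this goal.

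What the reply does not remove is the verb determine in 7.5, or the lack of any visible interval for the difference that the goal names.

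**Conclusion.** The concern holds in a limited form. The stated goal claims more than an observed best-of-three difference at 15 per arm can show, and the visible primary analysis omits the interval that would make this plain. On the reading that gives 73.4% a meaning, the criterion is met in about 34% of trials if every dose adds 10 points at 9% placebo. With smaller graded effects or with dropout as non-response the figure is about 23% to 28%; with the assumed higher placebo rates it is 41% to 43%.

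These rates rest on independent binomial arms of 15 and on effect sizes that the documents do not give. If placebo were treated as known at 9%, the +10 figure would be 14.0%, but the trial compares each dose with an observed 15-patient arm. The rates measure false encouragement and combine small arms with selection.

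A reader might also conclude that the goal should require a simultaneous lower bound above 25 points. That does not follow for an exploratory trial. With Bonferroni 98.3% Newcombe intervals and 1/15 on placebo, a dose would need at least 12/15, and the rule would be met in about 1% of trials under the protocol's own 40/30/20% against 9%.

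**What to change.** 1. SAP 7.4.1: report all three dose-minus-placebo differences in responder rate with 95% intervals, next to the per-arm intervals. Multiplicity-adjusted intervals are an optional supplement.
2. Protocol 7.5: replace the wording that the trial will determine a difference above 25%. Say that an observed best difference above 25 points will be treated as an exploratory signal, that it is the largest of three observed differences, and that it does not establish a true difference above 25 points.
3. Optional: beside the stated probability, give the probability of meeting the criterion under no effect and under smaller effects, with the method and assumptions used.

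The cost is one extra table and two changes of wording, with no added patients, visits or data. The downside is a less favourable description of what 15 patients per arm can show.

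### The 73.4% probability in Protocol 7.5 does not follow from the inputs printed beside it, which give 80.7%; state the missing assumption or restate the figure

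*Protocol*

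**What the plan says.** Protocol 7.5 plans 60 patients and says that no power calculation underlies the size. It then makes a qualitative claim: "The size of 15 patients per treatment arm is considered to be sufficient to detect differences between the different treatment groups and placebo" on the primary endpoint. The next paragraph narrows the goal to at least one dose beating placebo by more than 25% in responder rate, and sets out the assumptions: "Assuming that approximately 40%, 30%, 20% of patients in 80mg, 40mg, 20mg treatment groups, respectively, achieve at least 25% UPCR reduction at 12 weeks", with 9% on placebo. From these it concludes that the "sample size provides 73.4% probability for the difference in responder rates between at least one treatment arm and placebo to be greater than 25" percent.

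On method it says only: "Calculations were performed using R3.6.1". Protocol 7.4 confirms equal allocation, with three doses and "placebo in a 1:1:1:1 ratio stratified by use of corticosteroids". Section 7.5 states no dropout rate, evaluable number, approximation or prior. The SAP text supplied contains no sample-size calculation; its Introduction sends the reader back to the protocol for sample-size planning.

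**The concern.** A probability of this kind is fully determined by the arm sizes, the four response rates and the threshold, all of which are printed. A reader who puts them together does not get 73.4%. Either the figure is wrong, or it rests on something the protocol does not disclose.

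This is the only quantitative support for 15 per arm. The candidate explanations differ in meaning: an allowance for dropout would be prudent planning, whereas treating the placebo rate as known would ignore the sampling variability of a 15-patient control arm. The reader cannot tell which applies, if either does.

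A smaller point sits in the same section. The statement that 15 per arm suffices to detect differences between the treatment groups and placebo is broader than the at-least-one-dose goal that the calculation addresses.

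**Working it through.** **Inputs (Protocol 7.4 and 7.5).** Four arms of n = 15. Responder rates: 0.40 (80 mg), 0.30 (40 mg), 0.20 (20 mg), 0.09 (placebo). Success: the observed responder proportion on at least one dose exceeds placebo by more than 25 percentage points.

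**What the threshold means at n = 15.** Differences move in steps of 1/15: 3/15 = 20.0%, 4/15 = 26.7%. Success therefore means at least 4 more responders than placebo, and using ≥ instead of > changes nothing.

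**Formula.** Given k placebo responders, a dose fails if it has k + 3 or fewer. All doses share one placebo arm, so

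P = Σₖ Bin(k; 15, 0.09) × [1 − F₀.₄(k+3) × F₀.₃(k+3) × F₀.₂(k+3)],

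where Fₚ is the Binomial(15, p) cumulative distribution.

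| k | P(k) | F₀.₄ | F₀.₃ | F₀.₂ | P(success given k) | Product |
|---|---|---|---|---|---|---|
| 0 | 0.2430 | 0.0905 | 0.2969 | 0.6482 | 0.9826 | 0.2388 |
| 1 | 0.3605 | 0.2173 | 0.5155 | 0.8358 | 0.9064 | 0.3268 |
| 2 | 0.2496 | 0.4032 | 0.7216 | 0.9389 | 0.7268 | 0.1814 |
| 3 | 0.1070 | 0.6098 | 0.8689 | 0.9819 | 0.4797 | 0.0513 |
| 4 | 0.0317 | 0.7869 | 0.9500 | 0.9958 | 0.2556 | 0.0081 |
| 5 or more | | | | | | 0.0008 |

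The sum is **0.8072**. Simulation also gives 0.8072. The printed 0.734 is not reproduced; the gap is 80.7 − 73.4 = 7.3 points.

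**Single doses on the same inputs:** 80 mg 70.1%, 40 mg 43.1%, 20 mg 16.2%.

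**Can rounding or simulation error explain it?**
- All four rates moved half a point against the drug (39.5/29.5/19.5% vs 9.5%): 78.2%. Half a point in its favour (40.5/30.5/20.5% vs 8.5%): 83.1%.
- Standard error of a 1,000-run simulation: √(0.807 × 0.193 / 1000) = 0.0125. The gap is about 5.9 standard errors. It would be 2 standard errors only with about 117 runs.

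**Can another method on the printed inputs explain it?** Joint normal approximation 76.7%; with continuity correction 67.6% (1/2n) or 57.5% (1/n); comparisons treated as independent 85.8%. None gives 73.4%.

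**What comes close, but needs something not printed?**

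| Unstated assumption | Result |
|---|---|
| Placebo treated as known at 9% (a dose then needs at least 6 of 15) | 72.7% |
| 13 evaluable patients per arm | 72.2% |
| 10% dropout counted as non-response | 74.5% |
| About 11.6% dropout counted as non-response | 73.4% |
| Active rates each 2.5 points lower | 74.5% |
| Same, and placebo 9.5% | 73.1% |
| Active rates each about 2.9 points lower | 73.4% |
| Placebo rate about 11.7% | 73.4% |

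**Sensitivity to arm size, printed rates, equal arms:** 14 gives 76.8%, 15 gives 80.7%, 16 gives 68.6%, 17 gives 73.2%. The result is not monotone because the number of extra responders needed rises from 4 to 5 at n = 16.

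**The case against.** The active rates are round tens introduced as approximate, so half a point is a tighter tolerance than the text promises. Rates about 2.9 points lower would give exactly 73.4%, so the figure may be correct and merely under-documented. This stands in part: the documents cannot show that the sponsor's calculation was wrong. But all three rates would have to fall together by nearly 3 points, and if such rates were used they belong in the text.

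A second objection is that 80.7% is fragile. Fifteen is a local peak of a sawtooth, Protocol 3.1 and 4.1.3 plan only about 15 per group, and one patient more or fewer per arm lowers the probability by about 12 or 4 points. SAP 7.4.1 also counts patients without a week-12 value as non-responders. If the assumed rates refer to patients with data, some missingness would bring the true figure down towards 73.4%. This is a good reason not to print 80.7% without its conditions. It does not reconcile the printed figure, because Protocol 7.5 fixes 15 per arm and mentions no loss. The SAP rule is also in a later document and carries no assumed rate.

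Third, the trial is exploratory, Protocol 7.1 rules out confirmatory testing, and the error, if it is one, is on the cautious side. All true; this limits the weight of the point. The comment on detecting differences is secondary for the same reason, since the paragraph that follows does state the narrower goal.

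**Conclusion.** The concern holds. On the printed inputs the probability is 80.7%, not 73.4%. This rests on independent binomial arms, exactly 15 evaluable patients in each, no dropout, and the printed rates taken at face value. What is established is that the figure cannot be reproduced from what is stated; which undisclosed assumption produced it, if any, is unknown.

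The consequence is modest. The printed value understates the chance of meeting the criterion, and sample size, conduct and analysis do not depend on it. The broader claim about detecting differences is not supported for every dose, given chances of 43.1% for 40 mg and 16.2% for 20 mg.

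**What to change.** Check the original R calculation, then amend Protocol 7.5 in one of two ways:

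- **Keep 73.4% and state what yields it:** the evaluable number or dropout rate and how patients missing week 12 are counted, how the placebo rate is treated, or the unrounded rates.
- **Restate it as 80.7%** for 15 evaluable patients per arm with no dropout. Print the sensitivity beside it (76.8% at 14 per arm, 68.6% at 16) so that the favourable arm size is visible.

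In either case, say in the same sentence that this is the chance that at least one *observed* difference exceeds 25 percentage points, which at 15 per arm means at least 4 more responders than placebo. Replace the claim about detecting differences with wording limited to the goal, for example: *considered sufficient to explore whether at least one dose exceeds placebo*.

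The cost is one look at existing code and a few lines of text.
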